## BRIEF DESCRIPTION OF PROJECT

## A. Introduction & Rationale:

Plaque-induced gingivitis is an inflammatory disease restricted to the epithelial tissues surrounding the teeth. It is estimated that 86% of US population will be diagnosed with gingivitis at some point in their lives(Araujo et al. 2015; Eke, Wei, Borgnakke, Thornton-Evans, Zhang, Lu, McGuire, and Genco 2016b). The primary etiology of gingivitis, as well as most periodontal diseases, are a bacterial biofilm(Araujo et al. 2015; Chambrone et al. 2010). Although, not all individuals are equally susceptible to further tissue destruction, a prior history of gingivitis is required for patients to develop periodontitis(Page et al. 1997; Lang, Schätzle, and Löe 2009a; Jürgensen et al. 2012).

There is a consensus among the dental community that regular mechanical plaque control is enough for caries and periodontal disease prevention in most cases(Lang, Schätzle, and Löe 2009b). In the 1960's, Löe et al. clearly demonstrated the association

between plaque accumulation and gingivitis; furthermore, upon plaque removal, gingival health was re-established(Löe, Theilade, and Jensen 1965). However, research has shown that the average person brushes for 39 seconds each time(Macgregor and Rugg-Gunn 1979). Even more, most patients are not effective in interdental plaque removal(Lang, Schätzle, and Löe 2009b), hence the need for professional prophylaxis three to six times per year. With the premise that chemical agents are equally effective in preventing and reversing gingivitis, several studies investigated the efficacy of mouthwashes as plaque control agents in combination with mechanical regiments(Araujo et al. 2015). However, positive outcomes are often compromised by poor motivation and lack of compliance(). Therefore, delivery of chemical agents by a chewing gum might be an effective method to increase compliance in those patients with limited motor skills, unable or unwilling to perform regular oral hygiene.

Cetylpyridium Chloride (CPC) is a quaternary ammonia compound and a monocationic surfactant that is commonly used in mouthwashes as an antiplaque solution(Araujo et al. 2015). It can act as a detergent and has antiseptic properties, which are desirable characteristics of an ideal plaque control agent. Its ability to inhibit oral biofilm growth is due to the nonpolar region of the molecule that penetrates the cell membrane of the bacteria, leading to an osmotic dysregulation, resulting in loss of cytoplasmatic content, therefore bacterial cell death. In mouthwashes, CPC presents with a good absorption in the oral tissues and is has an anti-plaque, anti-calculus effect(Haps, Slot, and Berchier 2008), but has a low substantivity in the oral cavity of only 3 to 5 hours, which makes a chewing gum delivery an ideal vehicle for CPC. The purpose of this study is to determine the effect of four times a day mastication of antiplaque Chewing Gum on various factors associated with plaque accumulation and gingivitis.

**\*Hypotheses:** CPC based chewing gum in addition to tooth brushing will reduce plaque and gingivitis scores in adults similarly to tooth brushing alone.

**\*Specific aims: Aim 1:** to test the clinical plaque-inhibiting capacity of CPC based chewing gum, with mechanical oral hygiene, and placebo as a control. *Aim 2:* to evaluate the effects of using a CPC based chewing gum, with mechanical oral hygiene, to reduce gingivitis.

## B. Research design and methods:

#### **Study Design**

This study is a placebo-controlled, double-blind, randomized crossover study to evaluate the plaque and gingivitis reducing capacity of Cetylpyridium Chloride (CPC) based chewing gum.

#### **Study Population**

Test group will be composed of up to 73 dental, dental hygiene students, faculty, and staff, who will be recruited from the University of Texas Health Science Center at Houston School of Dentistry (*UTHealth School of Dentistry*). Those, who meet the inclusion criteria for the study, will meet with the investigators for additional information about the study and informed consent.

Plaque Index (PI)(Löe and Silness 1963) and Gingival Bleeding Index (GBI)(Lobene et al. 1989) and bleeding sites on probing (BOP) (Newbrun 1996) will be recorded at baseline for all selected subjects. After assessment, subjects will undergo oral prophylaxis to bring the plaque levels to zero. After oral prophylaxis subjects will be instructed on the proper brushing technique (Modified Bass techniques) and will be given either the test chewing gum or placebo formulation. The chewing gums will be packaged in similar fashion labeled only as sample A and sample B to ensure proper blinding of the product from the subjects and the examiner. All chewing gums will be supplied by Confadent oral technology, which will be sponsoring the current study. The test and control chewing gum will be dispensed to subjects along with a diary to record product usage and daily oral hygiene activity. All the subjects in both the groups will be given a soft bristled toothbrush and dental floss for use during the study. The study groups will be asked to refrain from all other unassigned forms of oral hygiene for the duration of the study. After four weeks, subjects will be recalled. GBI and PI will be evaluated at the end of 4 weeks using same indices.

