# **Exclusion Criteria:**

- Pregnant or breastfeeding women
- Patients taking long-term anti-microbial or anti-inflammatory drugs
- Patients unable or unwilling to provide informed consent
- Self-reported use of tobacco products
- Gross oral pathology, including widespread caries or chronic neglect, extensive restoration, pre-existing gross plaque or calculus, or soft or hard tissue tumor of the oral cavity
- Less than 26 teeth in the mouth
- Orthodontic appliances or removable partial dentures that will compromise the ability of the potential subject to participate in the study
- Periodontitis as indicated periodontal pockets greater than 5 millimeters on more than one site
- Inability to comply with assigned treatment regimen

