# C. Outcomes:

# Primary outcome:

The primary outcome of interest in this study is the efficacy of the antiplaque chewing gum in reducing existing supragingival plaque and gingivitis will be assessed.

**Plaque Index** - Plaque will be assessed using the Turesky Modification of the Quigley-Hein Plaque Index(Turesky, Gilmore, and Glickman 1970), where a score of 0 to

5 will be assigned to each facial and lingual non-restored surface of all teeth that are present with the exception of third molars at baseline and week 3 of the study, as follows:

Scores	Criteria
0	No plaque
1	Separate flecks of plaque at the cervical margin of the tooth
2	A thin continuous band of plaque (up to one mm) at the cervical margin of the tooth
3	A band of plaque wider than one mm but covering less than one- third of the crown of the tooth
4	Plaque covering at least one-third but less than two-thirds of the crown of the tooth
5	Plaque covering two-thirds or more of the crown of the tooth

Gingivitis will be assessed using both the Gingival Index (GI), where a score of 0 to

3 will be assigned to six teeth, representing six segments of jaws, at baseline and week 3

of the study according to the following criteria:

Scores	Criteria
0	Absence of inflammation.
1	Mild inflammation - slight change in color and little change in texture.
2	Moderate inflammation - moderate glazing, redness, edema, and hypertrophy. Bleeding on pressure.
3	Severe inflammation - marked redness and hypertrophy. Tendency to spontaneous bleeding. Ulceration.

In addition, the percent of bleeding sites on probing (BOP)(Ainamo and Bay 1975) as described in Ainamo & Bay, 1975, where each of 4 gingival areas (disto-buccal, midbuccal, mid-lingual, and mesio-lingual) around each tooth will be light probed and scored from 0 to 2 as follows:

Scores	Criteria
0	Absence of bleeding after 30 seconds
1	Bleeding after 30 seconds
2	Immediate bleeding

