#### Statistical analysis:

The Primary Aim is to evaluate the change in in the score of PI, GI, and BOP averaged across the teeth between the CPC based chewing gum and the placebo gum at day 21. Assume there is no carryover effect and no interactions between patients, treatments, and periods; a paired t-test is used to compute the sample size. To detect an effect size for CPC based chewing gum on the changes in the three outcomes at day 21 relative to baseline, with a within-subject correlation of 0.3 and a significance level of 0.05, the study requires 62 participants to achieve 80% power after Bonferroni correction for three tests. Considering a dropout rate of 15%, we need to recruit 73 participants.

Linear mixed model will be used to evaluate treatment effects on the three primary outcomes at day 21 compared to baseline independently, with Bonferroni correction. If normality of the outcomes does not hold, appropriate transformation or generalized estimating equation method can be used. Furthermore, the three outcomes could be analyzed simultaneously while accounting for the within-subject correlation. Similar analyses will be done for the secondary outcomes including changes from baseline to post-baseline efficacy assessment for day 21. Longitudinal data analysis will be used to analyze the data through day 0, 10, and 21, to see the pattern of the outcomes. Descriptive statistics will be provided for safety data. All analyses will be performed in SAS 9.4 (Cary, NC).

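### Plaque is cleaned to zero before gum use, yet the primary outcome speaks of reducing existing plaque, and the day-21 model does not fix its baseline, period and sequence terms

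*Combined protocol and SAP*

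**What the plan says.** **Design.** Study Population has plaque and gingival scores recorded at baseline. Then: "After assessment, subjects will undergo oral prophylaxis to bring the plaque levels to zero". Brushing instruction and gum follow. Only one prophylaxis is described. Randomization and allocation and Study period set out two 21-day periods with a washout, and Study period gives each period its own Day 1 baseline; neither section mentions cleaning. Inclusion Criteria ask participants to forgo optional procedures during the study and name prophylaxis as an example.

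**What is to be shown.** Aim 1 is "to test the clinical plaque-inhibiting capacity of CPC based chewing gum", and the stated purpose concerns "various factors associated with plaque accumulation and gingivitis". The primary outcome is the "efficacy of the antiplaque chewing gum in reducing existing supragingival plaque and gingivitis".

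**Analysis.** Statistical analysis states: "The Primary Aim is to evaluate the change in in the score of PI, GI, and BOP averaged across the teeth", comparing CPC gum with placebo gum at day 21. The model sentence reads: "Linear mixed model will be used to evaluate treatment effects on the three primary outcomes at day 21 compared to baseline independently", with Bonferroni correction. It lists no fixed effects, random effects or covariates. Period is mentioned only as an assumption for the sample size: "Assume there is no carryover effect and no interactions between patients, treatments, and periods". The sample size is 62 participants for 80% power by paired t-test, with the effect defined on changes from baseline, and 73 recruited for 15% dropout.

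**The concern.** Two things do not fit together.

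First, once plaque has been cleaned away there is no existing plaque for the gum to reduce. A lower day-21 plaque score on CPC gum shows slower re-formation. Removing plaque and inhibiting its return are different product claims, and the outcome section names the one that the design does not measure. This applies to the plaque index only: nothing in the documents says that prophylaxis sets the gingival index or bleeding on probing to zero.

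Second, the comparison with baseline is a comparison with the pre-cleaning score, and the plan leaves its form open. Baseline could be subtracted, used as a covariate or modelled as a repeated measure, and it could be the study-entry or the period-specific value. Period and sequence terms are neither included nor excluded. In a two-period crossover these choices define the primary analysis. If they are left open, the model can be chosen after the data are seen, and the default reading, a change score, is usually the less precise one.

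**Working it through.** **The plan's own figures.** 62/(1 − 0.15) = 72.9, so 73 reproduces. The 62 cannot be reproduced, because no effect size is given. A paired t-test with correlation 0.3 and two-sided 0.05/3 = 0.0167 gives 62 (power 80.4%) if the effect is assumed to be 0.5 SD: 0.5/√(2 × 0.7) = 0.423 SD of the paired difference. An effect of 0.455 SD with one-sided 0.0167, or 0.428 SD with two-sided 0.05, also leads to 62. The figure therefore does not reveal the scale or the test behind it.

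**Change score against covariate.** Let B and Y be the baseline and day-21 scores in a period, each with SD 1 (assumed). Let r be the correlation of B and Y within a period, and cBB, cYY and cBY the correlations across periods. For one participant's CPC-minus-placebo differences:

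- Var(Y difference) = 2(1 − cYY)
- Var(B difference) = 2(1 − cBB)
- Covariance = 2(r − cBY)
- Variance of change = 2(1 − cYY) + 2(1 − cBB) − 4(r − cBY)
- Variance with covariate = 2(1 − cYY) − [2(r − cBY)]²/[2(1 − cBB)]

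The first variance exceeds the second by Var(B difference) × (1 − slope)², where slope = covariance/Var(B difference). Subtraction fixes the slope at 1. Estimating the slope cannot raise the residual variance, and the two agree only when the true slope is 1.

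Example with r = 0.5 and all cross-period correlations 0.3:

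- change: 1.4 + 1.4 − 0.8 = 2.0
- covariate: 1.4 − 0.4²/1.4 = 1.286
- ratio: 2.0/1.286 = 1.56

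If 62 pairs give 80.0% power for change (two-sided 0.05/3, 61 df), the noncentrality is 3.314. For the covariate analysis it is 3.314 × √ratio on 59 df.

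| Cross-period correlations (assumed) | r | Change | Covariate | Ratio | Covariate power |
|---|---|---|---|---|---|
| all 0.3 | 0.3 | 2.80 | 1.400 | 2.00 | 98.5% |
| all 0.3 | 0.5 | 2.00 | 1.286 | 1.56 | 94.9% |
| all 0.3 | 0.7 | 1.20 | 0.943 | 1.27 | 89.5% |
| all 0.3 | 0.8 | 0.80 | 0.686 | 1.17 | 86.4% |
| cBY = 0.3r, others 0.3 | 0.3 | 1.96 | 1.274 | 1.54 | 94.7% |
| cBY = 0.3r, others 0.3 | 0.5 | 1.40 | 1.050 | 1.33 | 91.0% |
| cBY = 0.3r, others 0.3 | 0.8 | 0.56 | 0.504 | 1.11 | 84.5% |
| cBB = 0.6, others 0.3 | 0.5 | 1.40 | 1.200 | 1.17 | 86.4% |
| cBB = 0.6, others 0.3 | 0.7 | 0.60 | 0.600 | 1.00 | 79.9% |

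In the first row the slope is 0, so the whole gain comes from not subtracting. In the last row the slope is 1, the worst case. There, a simulation of 20,000 trials with a period term gave 79.3% for the covariate model against 80.3% for change. In simulations without carryover, bias was at most 0.002 SD and type I error was 0.0160 for change and 0.0169 for the covariate model (nominal 0.0167).

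**Period term.** With an effect of 0.5 SD, 62 completers in balanced sequences and a paired difference variance of 1.4, leaving out a period difference p (in SD of a single score) raises that variance to 1.4 + p². Power falls from 80.4% to about 78%, 73% or 53% for p = 0.25, 0.5 or 1.0. The documents give no value for p. A period difference is plausible, because the period-2 baseline follows brushing instruction, at least one cleaning, a gum period and a washout.

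**The case against.** The strongest reply is that little harm follows. Change from baseline is the plan's declared measure, the missing terms are not ruled out, and any prophylaxis effect common to both gums cancels in the randomised comparison. All of that stands.

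Two stronger readings are tempting, and neither is supported. A reader might infer that the gum comparison is biased by the cleaning step; it is not, if cleaning is applied alike under both gums. A reader might also infer that 62 is too few. The plan defines the effect on the changes, so 62 may already allow for baseline noise.

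Other objections narrow the point:

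- Re-formed plaque is certain only for period 1. If cleaning is not repeated, period 2 may start with plaque present, so the outcome can be reworded only after the passages are reconciled.
- The exclusion of "pre-existing gross plaque or calculus" might seem to support the contradiction. It does not: it covers gross plaque only, and people with ordinary plaque remain eligible.
- The size of the gain depends on correlations that the documents do not give, and the covariate model can lose slightly.
- The period-2 baseline is measured after period-1 treatment, so adjusting for it relies on the plan's no-carryover assumption. Subtracting it relies on the same assumption.

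Study Population also has a four-week recall, which conflicts with the 21-day periods elsewhere. That needs reconciling too but is a separate matter.

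**Conclusion.** The point holds as a low-cost improvement. The primary outcome's wording does not match a design that cleans plaque before gum use, at least in period 1, and whether cleaning precedes period 2 is unstated. The primary model is under-specified for a crossover: the form of the baseline and the period and sequence terms are open.

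With equal SDs, two-sided 0.05/3, 62 complete pairs and 80% power for change, the change-to-covariate variance ratio is about 1.0 to 2.0 and covariate power about 80% to 98%. These are illustrations over assumed correlations, not estimates for this trial. What is firm is that estimating the slope usually gains precision and at worst costs about 1 power point.

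**What to change.** 1. **Outcome.** Reconcile Study Population, Inclusion Criteria, Randomization and allocation, and Study period on whether prophylaxis precedes each period. If it precedes both, reword the primary plaque outcome as plaque re-accumulation (inhibition) after prophylaxis. Limit this to the plaque index.

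2. **Model.** For each primary outcome, pre-specify a linear mixed model of the day-21 score with treatment, period and sequence as fixed effects and participant as random effect. Use that period's baseline and the participant's mean baseline as covariates. For participants with period 1 only, use the available baseline as the mean, so that they stay in the model. State that the adjustment relies on no carryover. Keep change from baseline as the secondary analysis that the plan already lists.

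3. **Sample size.** State whether the effect behind 62 is on the change scale or the day-21 scale.

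**Cost.** Text changes to the outcome, design and analysis sections. A Day 1 baseline and a day-22 visit are already planned in each period, so no visits, measurements or participants are added. The primary measure does move from change to the adjusted day-21 score, which should be recorded as an amendment before unblinding. The statistical cost is about two degrees of freedom.

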# Randomization and allocation:

Randomization will be carried out using a computer-generated random allocation

table assigning the participants to one of study groups as follows:

Arms	Assigned Interventions
Experimental: CPC 0.09% +	Dietary Supplement: CPC 0.09% + Xylitol
Xylitol chewing gum A	

		All subjects will be instructed to chew four times a
		day, for at least 60 seconds, after which they
		expectorated.
		Other Name: CPC-Xylitol complex
Experimental: Xy	litol only	Dietary Supplement: Xylitol
chewing gum B		All subjects will be instructed to chew four times a
		day, for at least 60 seconds, after which they
		expectorated.
		Other Name: Xylitol only

Half of the eligible participants will be randomly assigned to get CPC gum in the first treatment period (21 days), a wash-out period of 21 days, and then a placebo gum in the second treatment period (21 days). The other half would be assigned to follow the same schedule but with the treatment reversed. A statistician will perform the randomization whereas the project leader will distribute the chewing gums and instructions after a list generated as described.

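### The packs are blinded by the letters A and B, yet the arms table prints A against CPC and B against xylitol only, and nothing in the protocol separates the two sets of letters

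*Combined protocol and SAP*

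**What the plan says.** The Study Design section of the Combined protocol and SAP describes a double-blind crossover trial with a placebo gum. The means of blinding is given under Study Population: "The chewing gums will be packaged in similar fashion", and the packs are "labeled only as sample A and sample B to ensure proper blinding of the product from the subjects and the examiner". No other code on the packs is described.

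The arms table under Randomization and allocation has one row per gum. The row that begins with CPC 0.09% continues "Xylitol chewing gum A"; the xylitol-only row carries the letter B. The table is split over lines in the text available, but each letter can still be read in its row.

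The same section sets out the crossover: "Half of the eligible participants will be randomly assigned to get CPC gum in the first treatment period", with placebo in the second period, and "The other half would be assigned to follow the same schedule but with the treatment reversed". On roles it says: "A statistician will perform the randomization whereas the project leader will distribute the chewing gums", working from the generated list. It does not say who holds the key to the letters, whether the project leader is blinded, or whether that person is separate from the examiner.

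**The concern.** A two-letter code blinds only while the meaning of the letters is kept from the people who see them. Here the protocol appears to print that meaning, in a document that study staff would be expected to read.

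The outcomes leave room for knowledge of treatment to matter. Under Primary outcome, plaque (0 to 5), gingival inflammation (0 to 3) and bleeding on probing (0 to 2) are all scored by an examiner. Under Secondary Outcomes, the principal investigator judges whether soft-tissue changes might be due to the gum. Participants control their own brushing and flossing and keep "a diary to record product usage and daily oral hygiene activity". They are "up to 73 dental, dental hygiene students, faculty, and staff" of one dental school, so some may know one another and could compare packs. Knowing the treatment could influence scoring, attribution or hygiene effort.

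**Working it through.** The plan gives no figure on this point, so the check sets the sections side by side.

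1. **What is on the pack.** Study Population gives the letters A and B and says that these are the only labels. No section mentions a participant number, a kit number, or letters scrambled by participant or by period.

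2. **What is in the table.** The arms table under Randomization and allocation gives A = CPC 0.09% + xylitol and B = xylitol only.

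3. **First inference: pack A is table A.** This is not stated. The packs speak of samples and the table of chewing gums. But the same two letters are attached to the same two gums in one short protocol, and no sentence says that they were assigned separately.

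4. **Second inference: a letter means the same gum for everyone.** This is not stated either. It follows most simply from the packs carrying nothing but one of two letters, with no participant-level code described.

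5. **What follows if both inferences hold.** The table plus a participant's current letter gives the current gum. Because each sequence is CPC then placebo, or the reverse, the current gum also fixes the gum in the other period. The same printed key would serve for every participant whose letter became known.

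6. **Who would need to hold what.** Unblinding requires one person to have both the table and a letter.
   - *Subjects* see their own pack. No section gives them the protocol.
   - *The examiner* may well know the protocol. No section has the examiner handle packs or learn letters.
   - *The project leader* distributes the gum, so is likely to have both. No section says whether this person also examines.

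Step 6 is where the documents stop. They show a weakness in the written procedure and do not allow a count of people or assessments affected.

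**The case against.** The strongest reply is that the link between pack and table is inferred. The table letters may be no more than arm names, with the pack letters assigned separately. The stated purpose of the pack labels, to blind subjects and examiner, fits that better than a code whose key is printed a page or so later. It is also not stated that one letter means one gum for all participants. Finally, the statistician randomises and the project leader dispenses, so the examiner may never see a letter. The consent pages were not available, so what subjects are told about A and B cannot be judged.

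Much of this stands. Both inferences must be presented as inferences, and the stated purpose is some evidence against the first. Recruitment from one dental school is context, not evidence that anyone had access to the protocol. But identical letters remain the simpler reading. One sentence would have separated the two sets, and there is none. The division of roles helps only if the dispenser and the examiner are different people, which is not stated.

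A reader might go further and infer that the blind was broken, that every participant's periods were exposed, or that the results lean towards CPC. The documents support none of these. A shared key makes every period decodable by someone who also has every letter; it does not show that such a person exists among the examiners or subjects.

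**Conclusion.** The point holds as a weakness in the written blinding procedure: the label that is meant to conceal the product matches, letter for letter, the label that the arms table uses to identify it. It rests on two assumptions that the documents suggest but do not state: that the pack letters are the table letters, and that each letter means the same gum for all participants.

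Exposure may be zero. No size or direction of bias can be derived, and none should be quoted. It is still worth correcting, because the main outcomes are examiner-rated, the trial claims to be double-blind, and the correction is cheap.

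**What to change.** - Remove the letters A and B from the arms table under Randomization and allocation.
- Put new codes on the packs that match no arm label printed anywhere in the protocol. Deleting the table letters alone would not help with anyone who has already read this version.
- As a minimum, use new neutral codes. The stronger option is participant-and-period kit numbers generated by the randomising statistician, because one leaked code then does not decode everyone.
- State that the statistician holds the key until database lock, with the supplier having it only as far as packing requires.
- State that the project leader dispenses by code only, from a list that does not name the gum, and say whether the project leader is separate from the examiner.

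The cost is a short protocol edit, relabelling and slightly more dispensing logistics. Kit numbers would come to at most 2 periods x 73 participants = 146; the number of packs behind each is not stated. No new role is needed, since a statistician already performs the randomisation, and no visit, outcome or sample size changes.

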## Secondary Outcomes:

Changes from baseline to post-baseline efficacy assessment will be recorded for all parameters.

The antiplaque **chewing gum safety** will be evaluated; the oral soft (OST) and oral hard tissues (OHT) will be examined. Changes from baseline, such as soft tissue erythema, ulceration, and sloughing, will be noted and assessments will be made by the principal investigator as to whether they might be attributable to the antiplaque chewinggum.

Objective observation of **Discoloration of teeth** will be recorded using a Vita 3D scale. Changes on baseline (day 1) and day 22 and will be annotated as none, slight to obvious.

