## Study period:

The study period will be comprised of two periods of 21 days with a washout period in between. In each 21 days' period, there are three study visits: 1) Baseline Day

1, 2) Day 11 (after ten days of use), and 3) Day 22 (after 21 days of use – completion of the study). An additional screening visit will be required, and may or may not be combined with baseline visit, according to patients' preference.

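### No between-visit symptom record is described, so short-lived mouth lesions can be missed and their onset goes undated

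*Combined protocol and SAP*

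**What the plan says.** All references are to the combined protocol and SAP.

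- **Secondary Outcomes** makes gum safety an outcome and gives the method: "the oral soft (OST) and oral hard tissues (OHT) will be examined". It continues: "Changes from baseline, such as soft tissue erythema, ulceration, and sloughing, will be noted". The principal investigator then judges whether a change might be due to the gum. The visits for this examination are not named. The only days named in that section, Day 1 and Day 22, belong to tooth discoloration.
- **Study period** schedules a Day 1 baseline visit in each period, followed by "2) Day 11 (after ten days of use), and 3) Day 22 (after 21 days of use – completion of the study".
- **Randomization and allocation** separates the two periods by "a wash-out period of 21 days". No visit within the washout is described.
- **Study Population** says the gum is "dispensed to subjects along with a diary to record product usage and daily oral hygiene activity".
- **Statistical analysis** says safety data will be summarised descriptively. It defines no safety analysis set.

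**The concern.** The named harms can be brief, the gum is chewed four times a day, and the described way of finding a lesion is to look in the mouth at a visit. The best-case gaps between examinations within a period are 10 and 11 days. If the tissues are examined only at the start and end of a period, the gap is 21 days. The participant fills in a diary throughout, but as described it asks about gum use and oral hygiene and not about the mouth.

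Two things are at stake. First, a low count of lesions could reflect either few lesions or few occasions on which they could be seen, and the safety table could not tell these apart. Second, the investigator is asked to judge attribution in a crossover, where it matters when a lesion began and which gum was then in use. A lesion found at a visit could have begun at any time since the previous examination, and one found on Day 1 of period 2 could have begun under the first gum or in the washout.

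**Working it through.** **The plan's own figure.** The only stated number that touches this point is the allowance for early leavers: "Considering a dropout rate of 15%, we need to recruit 73 participants". It reproduces: 62 / (1 − 0.15) = 72.94, rounded up to 73, so about 73 − 62 = 11 early leavers are expected. It is not used in the calculation below.

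**Inputs from the documents.** There are 21 days of use per period, with visits after 10 and after 21 days of use (Study period). The gaps are therefore 10 and 21 − 10 = 11 days.

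**Assumptions, not in the documents.** A lesion starts at a time uniform over the 21 days of use, is visible for d days and then heals. It is always recognised if visible at an examination. Because d is unknown, a range is shown.

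**Formulas.** A lesion is seen at an examination if it started within the d days before it.

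- Examinations after 10 and 21 days of use: share seen = (min(d, 10) + min(d, 11)) / 21.
- Examination at Day 22 only: share seen = min(d, 21) / 21.

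| d (days visible) | Days 11 and 22 | Day 22 only |
|---|---|---|
| 3 | 6/21 = 29% | 3/21 = 14% |
| 5 | 10/21 = 48% | 5/21 = 24% |
| 7 | 14/21 = 67% | 7/21 = 33% |
| 10 | 20/21 = 95% | 10/21 = 48% |
| 11 | 21/21 = 100% | 11/21 = 52% |

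The Days 11 and 22 column is the best case that the visit schedule allows, because the plan does not commit to a tissue examination at Day 11.

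**A timing conflict that bears on this.** Study Population recalls participants after four weeks, whereas Randomization and allocation and Study period use 21 days. These passages must be reconciled, since the answer changes the examination interval.

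**The case against.** The strongest reply is that the point rests on silence. The diary's purpose is given in one clause and the form itself is not in the documents. Nothing excludes spontaneous reports, and consent pages, which were not available for this check, may ask participants to report problems. This stands. The supportable statement is that no between-visit symptom collection is described, not that none will happen. A reader might infer that brief lesions are necessarily missed. The table shows otherwise: a lesion that overlaps an examination is seen.

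The duration model can also be challenged. Irritation that persists under continued chewing would be caught, and with both examinations detection is complete from 11 days on. That is fair, and it is why a range is given.

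Both gums share the same visits, so missed lesions lower both counts and the ratio between gums need not be distorted. This also stands if lesions last equally long with either gum. Even then the absolute counts, and the absolute difference between gums, shrink by the share seen.

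A reader might further infer that harms in people who stop early drop out of the safety table. The documents do not support that. They set no completers-only safety set, and 62 is the requirement for the efficacy tests. Someone who leaves after Day 11 may already have been examined once on that gum, and someone who leaves in the washout or period 2 may have both examinations for the first gum. No exit examination is described, but the size of any loss cannot be worked out from the plan.

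Nor should Day 22 be read as the stated time of the tissue examination; that day is given only for discoloration.

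**Conclusion.** The point holds as a limited weakness in safety data collection. The plan describes tissue examinations at unspecified visits and a diary of usage and hygiene, so erythema, ulceration or sloughing lasting less than about 10 days can be missed, and onset is not recorded. Under uniform onset and perfect recognition, the two-examination schedule would see 29% to 67% of lesions visible for 3 to 7 days. A Day 22 examination alone would see 14% to 33%. These figures depend on assumed lesion durations and indicate scale only; they are not estimates for this gum.

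Neither a biased comparison between gums nor a systematic loss of early leavers' harms can be shown from the text. Safety is a secondary, descriptive outcome. The point is a worthwhile, inexpensive improvement.

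**What to change.** Add one daily line to the existing diary: any soreness, redness, ulcer or peeling in the mouth today (yes/no, and where). Review the entries at the existing visits, assign each to the gum in use at onset, and report them by gum in the descriptive safety table beside the examination findings. State in Secondary Outcomes at which visits the soft and hard tissues are examined. Examining early leavers who are willing is an optional extra.

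The cost is one diary line and a few minutes at visits that already take place. The downside is more minor self-reported complaints to tabulate, some due to the baseline probing and prophylaxis. Two things limit that. Half the participants start on each gum, so complaints following the first baseline procedures should fall about equally on both. The dated entries also show which complaints came soon after those procedures.
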